**8.3.2.2. Assessment of severity**

Intensity of the following AEs will be assessed as described:

The physician will assess the maximum intensity that occurred over the duration of the event for all AEs (SAEs) recorded during the PMS. The assessment will be based on the physician's clinical judgement.

**CONFIDENTIAL**

208710 (EPI-HPV-077 VS KR PMS)  
Protocol Amendment 1 Final

The intensity of each AE and SAE recorded in the CRF or SAE Report Form, as applicable, should be assigned to one of the following categories:

- 1 (mild) = An AE/SAE which is easily tolerated by the subject, causing minimal discomfort and not interfering with everyday activities.  
For fever:  $\geq 37.5^{\circ}\text{C}$  to  $\leq 38.0^{\circ}\text{C}$  (Oral/Axillary/ Tympanic temperature).
- 2 (moderate) = An AE/SAE which is sufficiently discomforting to interfere with normal everyday activities.  
For fever:  $>38^{\circ}\text{C}$  to  $\leq 39.0^{\circ}\text{C}$  (Oral/Axillary/ Tympanic temperature).
- 3 (severe) = An AE/SAE which prevents normal, everyday activities (in a young child, such an AE would, for example, prevent attendance at school/kindergarten/a day-care centre and would cause the parent(s)/LAR(s) to seek medical advice).  
For fever:  $>39.0^{\circ}\text{C}$  (Oral/Axillary/ Tympanic temperature).

An AE that is assessed as Grade 3 (severe) should not be confused with a SAE. Grade 3 is a category utilised for rating the intensity of an event; and both AEs and SAEs can be assessed as Grade 3. An event is defined as 'serious' when it meets one of the pre-defined outcomes as described in Section 8.1.3.

### **8.3.2.3. Assessment of causality**

The Physician is obligated to assess the relationship between *Cervarix* and the occurrence of each AE/SAE. The Physician will use clinical judgement to determine the relationship. Alternative plausible causes, based on natural history of the underlying diseases, concomitant therapy, other risk factors and the temporal relationship of the event to the administration of *Cervarix* will be considered and investigated. The Physician will also consult the local Prescribing Information (Summary of Product Characteristics, SPC) to ensure an accurate assessment.

There may be situations when a SAE has occurred and the Physician has minimal information to include in the initial report to GSK Biologicals. However, it is very important that the Physician always makes an assessment of causality for every event prior to submission of the SAE to GSK Biologicals. The Physician may change his/her opinion of causality in light of follow-up information, and update the SAE information accordingly. The causality assessment is one of the criteria used when determining regulatory reporting requirements.

In case of concomitant administration of multiple vaccines, it may not be possible to determine the causal relationship of general AEs to the individual vaccines administered. The Physician should, therefore, assess whether the AE could be causally related to vaccination rather than to the individual vaccines.

**CONFIDENTIAL**

208710 (EPI-HPV-077 VS KR PMS)  
Protocol Amendment 1 Final

Causality of AEs should be assessed by the Physician using the following question:

Is there a reasonable possibility that the AE may have been caused by *Cervarix*?

If an event meets the criteria to be determined as ‘serious’ (see Section 8.1.3), additional examinations/tests will be performed by the Physician in order to determine ALL possible contributing factors applicable to each SAE.

Possible contributing factors include:

- Medical history
- Other medication
- Other procedure not required by the protocol
- Lack of efficacy of the vaccine(s), if applicable.
- Erroneous administration
- Other cause (specify).

Assessment of causality of these AEs will be done to reflect the requirement of MFDS (Korea) to assess the relationship of the AEs.

NOTE: The use of the term “drug” here refers to *Cervarix*.

As per MFDS (Korea) requirements, causality will be assessed as:

1. Certain:

The relationship of the administration and use of the drug is reasonable and it is not able to be explained by other medication, chemical substances or concomitant disease, it shows clinically reasonable response on withdrawal of the drug, the decisive case in the pharmacological or phenomenological aspect on re-challenge of the drugs if needed.

2. Probable/Likely:

The temporal sequence of the administration and use of the drug is appropriate and it does not seem that it is accompanied by other medications, chemical substances or concomitant disease, in the case that shows clinically appropriate response on withdrawal of the drug (no information for re-challenge).

3. Possible:

The temporal sequence of the administration and use of the drug is appropriate but it is also able to be explained by other medications, chemical substances or concomitant disease, and information related to withdrawal of the drug is insufficient or vague.

4. Unlikely:

It is a transitory case which may not have causality with the administration and use of the drug, it is also able to be explained reasonably by other medications, chemical substances or latent disease.

**CONFIDENTIAL**208710 (EPI-HPV-077 VS KR PMS)  
Protocol Amendment 1 Final

## 5. Conditional/Unclassified:

In the case that more information is needed for a proper evaluation or additional information is under review.

## 6. Unassessible/Unclassifiable:

In the case that could not be judged due to insufficient or conflicting information and no way to complement or validate.

If the physician judges that the causal relationship is 1. Certain, 2. Probable/Likely, 3. Possible, 5. Conditional/Unclassified, or 6. Unassessible/Unclassifiable, they should classify the relevant event as an ADR according to the GSK Reporting Procedure and prepare an ADR Report.

**8.3.2.4. Assessment of the outcomes**

Outcome of any non-serious AE occurring within 30 days post-vaccination or any SAE reported during the entire PMS will be assessed as:

- Recovered/resolved.
- Not recovered/not resolved.
- Recovering/resolving.
- Recovered with sequelae/resolved with sequelae.
- Fatal.
- Unknown.

**8.3.2.5. Medically attended visits**

For each adverse event the subject experiences, subject's parent(s)/LAR(s) will be asked if the subject received medical attention defined as hospitalisation or an otherwise unscheduled visit to or from medical personnel for any reason, including emergency room visits. This information will be recorded in the CRF.

**8.4. Reporting of SAEs, Pregnancies and other events *related to Cervarix* (Amended: 14 May 2018)****8.4.1. Prompt reporting of SAEs related to PMS participation/ related to Cervarix, pregnancies and other events to GSK**

SAEs that occur in the time period defined in Section 8.3.1 will be reported promptly to GSK within the timeframes described in [Table 5](#) once the physician determines that the event meets the protocol definition of an SAE.

**CONFIDENTIAL**208710 (EPI-HPV-077 VS KR PMS)  
Protocol Amendment 1 Final

Non-serious AEs related to the vaccine that occur in the time period defined in Section 8.3.1 will be reported promptly to GSK Biologicals within the timeframes described in **Table 5** once the physician determines that the event meets the protocol definition for that event.

Pregnancies that occur in the time period defined in Section 8.3.1 will be reported promptly to GSK within the timeframes described in **Table 5** once the physician becomes aware of the pregnancy. The subject will be followed to determine the outcome of the pregnancy.

**Table 5 Time frames for submitting SAEs and other events reports to GSK Biologicals**

Type of Event	Initial Reports		Follow-up of Relevant Information on a Previous Report	
	Time Frame	Documents	Time Frame	Documents
All SAEs	24 hours*	SAE report	24 hours*	SAE report
All ADRs	5 days **	ADR Report Form	5 days **	ADR Report Form
Pregnancies	2 weeks *	Pregnancy Report Form	2 weeks *	Pregnancy Report Form

\* Time frame is allowed after receipt or awareness of the information.

\*\* Recommended Time frame for ADR reporting for the physicians after the awareness of the information.

#### **8.4.3. Regulatory reporting requirements for SAEs**

The physician will promptly report all SAEs to GSK in accordance with the procedures detailed in Section 8.4.1. GSK Vaccines has a legal responsibility to promptly notify, as appropriate, both the local regulatory authority and other regulatory agencies about the safety of a product under surveillance. Prompt notification of SAEs by the physician to the PMS Contact for Reporting SAEs is essential so that legal obligations and ethical responsibilities towards the safety of other subjects are met.

**CONFIDENTIAL**208710 (EPI-HPV-077 VS KR PMS)  
Protocol Amendment 1 Final**8.4.4. Completion and transmission of SAE reports to GSK Biologicals**

Once a physician becomes aware that an SAE has occurred in a PMS subject, she/he will report the information to GSK within 24 hours. The SAE Report Form will always be completed as thoroughly as possible with all available details of the event, signed by the physician (or designee), and forwarded to GSK within the designated time frames. If the physician does not have all information regarding an SAE, he/she will not wait to receive additional information before notifying GSK of the event and completing the form. The form will be updated when additional relevant information is received and forwarded to GSK WITHIN 24 HOURS.

The physician will always provide an assessment of causality at the time of the initial report. The causality assessment may change depending on the availability of additional/follow-up information.

Facsimile (Fax) transmission *or e-mail delivery* of the SAE Report Form is the preferred method to transmit this information to the Contact for Reporting SAEs. In rare circumstances and due to failure of facsimile *or electronic* equipment, notification by telephone is acceptable, with a copy of the SAE Report Form sent by overnight mail. Initial notification via the telephone does not replace the need for the physician to complete and sign the SAE Report Form within 24 hours.

In the event of a death determined by the physician to be related to vaccination, sending of the fax *or e-mail* must be accompanied by telephone call to the PMS Contact for Reporting SAEs.

**8.4.5. Completion and transmission of non-serious AEs related to Cervarix reports to GSK**

Once a physician becomes aware that a non-serious AE related to vaccine has occurred in a PMS subject, the physician (or designee) must complete an **ADR** Report and forward it to GSK within 5 calendar days. The report will always be completed as thoroughly as possible with all available details of the event and then dated and signed by the physician (or designee). Even if the physician does not have all information regarding an AE, the report should still be completed and forwarded to GSK within 5 calendar days. Once additional relevant information is received, the report should be updated and forwarded to GSK within two weeks.

The physician will always provide an assessment of causality at the time of the initial report.

Fax transmission *or e-mail delivery* is the preferred method to forward the paper **ADR** Report to the PMS Contact for Reporting SAEs. In absence/ dysfunction of fax equipment *or electronic*, the PMS Contact for Reporting SAEs must be notified by telephone within 5 calendar days. As soon as the fax equipment *or electronic* is working again, the physician (or designee) must fax *or e-mail* the report to the PMS Contact for Reporting SAEs within 5 calendar days.

**CONFIDENTIAL**208710 (EPI-HPV-077 VS KR PMS)  
Protocol Amendment 1 Final

#### **8.4.6. Completion and transmission of pregnancy reports to GSK Biologicals**

Once the physician becomes aware that a subject is pregnant, the physician (or designee) must complete, date and sign a paper pregnancy notification report and fax *or e-mail* it to the PMS Contact for Reporting SAEs (refer to the local PMS contact information document) **WITHIN 2 WEEKS**.

Note: Conventionally, the estimated gestational age (EGA) of a pregnancy is dated from the first day of the last menstrual period (LMP) of the cycle in which a woman conceives. If the LMP is uncertain or unknown, dating of EGA and the estimated date of delivery (EDD) should be estimated by ultrasound examination and recorded in the pregnancy report.

#### **8.5. Follow-up of AEs and SAEs (Amended: 14 May 2018)**

After the initial AE/SAE report, the physician is required to proactively follow each subject and provide further information to GSK Biologicals on the subject's condition.

All SAEs documented at a previous visit/contact and designated as not recovered/not resolved or recovering/resolving will be reviewed at subsequent visits/contacts until the end of the PMS.

All AEs documented at a previous visit/contact and designated as not recovered/not resolved or recovering/resolving will be reviewed at subsequent visits/contacts up to 30 days (**Day 1 to Day 30**) after the last dose of *Cervarix* administered during the subject's participation in the PMS.

Physicians will follow-up subjects:

- With SAEs or subjects withdrawn from the PMS as a result of an AE, until the event has resolved, subsided, stabilised, disappeared, or until the event is otherwise explained, or the subject is lost to follow-up.
- Or, in the case of other non-serious AEs, until or they are lost to follow-up.

Clinically significant laboratory abnormalities will be followed up until they have returned to normal, or a satisfactory explanation has been provided. Additional information (including but not limited to laboratory results) relative to the subsequent course of such abnormalities noted for any subject must be made available to the PMS Monitor.

GSK Biologicals may request that the physician perform or arrange for the conduct of additional clinical examinations/tests and/or evaluations to elucidate as fully as possible the nature and/or causality of the AE or SAE. The physician is obliged to assist. If a subject dies during participation in the PMS or during a recognised follow-up period, GSK Biologicals will be provided with a copy of any available post-mortem findings, including histopathology.

**CONFIDENTIAL**208710 (EPI-HPV-077 VS KR PMS)  
Protocol Amendment 1 Final

### **8.5.1. Follow-up of pregnancies**

Pregnant subjects will be followed to determine the outcome of the pregnancy. At the end of the pregnancy, whether full-term or premature, information on the status of the mother and child will be forwarded to GSK Biologicals using the paper pregnancy follow-up report and the *SAE* Report if applicable. Generally, the follow-up period does not need to be longer than six to eight weeks after the estimated date of delivery.

Regardless of the reporting period for SAEs for this PMS, if the pregnancy outcome is an SAE, it should always be reported as an SAE.

### **8.6. Treatment of AEs**

Treatment of any adverse event is at the sole discretion of the physician and according to current good medical practice. Any medication administered for the treatment of an AE should be recorded in the subject's CRF.

## **9. EFFICACY ASSESSMENT**

Efficacy of a vaccine is assessed by the reduction in the occurrence of the disease targeted by the vaccine in people immunized with the vaccine comparing to those not vaccinated. A drug use investigation will be implemented within the routine clinical setting to collect unspecified safety and efficacy data of the drug through the PMS period. It will be difficult for the physicians to request the subject after vaccination to revisit for assessment and/or laboratory testing not deemed necessary in normal clinical practice due to the physical, logistic, and economic burden to the subject. Therefore, the efficacy assessment of *Cervarix* would likely be omitted in this drug use investigation.

## **10. SUBJECT COMPLETION AND WITHDRAWAL**

### **10.1. Subject completion**

Subjects who have completed 30-day follow-up after at least one dose, regardless of the number of doses are considered to have completed the PMS.

### **10.2. Subject withdrawal (Amended: 14 May 2018)**

Subjects who are withdrawn because of SAEs/AEs must be clearly distinguished from subjects who are withdrawn for other reasons. Physicians will follow subjects who are withdrawn as result of a SAE/AE until resolution of the event (see Section 8.5).

Withdrawals will not be replaced.

**CONFIDENTIAL**208710 (EPI-HPV-077 VS KR PMS)  
Protocol Amendment 1 Final**10.2.1. Subject withdrawal from PMS**

From an analysis perspective, a ‘withdrawal’ from the PMS refers to any subject who did not come back for the concluding visit/was not available for the concluding contact foreseen in the protocol.

All data collected until the date of withdrawal/last contact of the subject will be used for the analysis.

A subject is considered a ‘withdrawal’ from the PMS when no PMS procedure has occurred, no follow-up has been performed and no further information has been collected for this subject from the date of withdrawal/last contact.

Physicians will make **attempts** to contact those subjects who do not return for scheduled visits or follow-up.

Information relative to the withdrawal will be documented in the CRF. The physician will document whether the decision to withdraw a subject from the PMS was made by the subject’s parent(s) or LAR(s), or by the physician, as well as which of the following possible reasons was responsible for withdrawal:

- Serious adverse event.
- Non-serious adverse event.
- Protocol violation (specify).
- Consent withdrawal, not due to an adverse event.
- Lost to follow-up.
- Death.
- Other (specify).

**11. STATISTICAL METHODS****11.1. Endpoints (Amended: 14 May 2018)**

- Occurrence of AEs during the 30-day (**Day 1 to Day 30**) follow-up period after each vaccine dose.
- Occurrence of SAEs reported throughout the PMS period up to 30 days (**Day 1 to Day 30**) after the last dose administered during the subject’s participation in the PMS.

**CONFIDENTIAL**208710 (EPI-HPV-077 VS KR PMS)  
Protocol Amendment 1 Final

## 11.2. Determination of sample size

According to MFDS (Korea) regulation requirement, at least 600 evaluable subjects will be recruited for the PMS. Therefore, 660 subjects are expected to be enrolled through the PMS period considering the dropout rate of 10% (out of 600 subjects). Depending on the status, the enrolment plan can be adjusted.

**Table 6** presents the exact two-sided 95% confidence interval for a sample size of 600 subjects.

**Table 6      Exact two-sided 95% CI for the percentage of subjects reporting at least one symptom with a sample size of 600 subjects**

Observed rate expressed as a percentage (number of subjects reporting at least one symptom*)	Exact two-sided 95% CI for this observed rate for a sample size of 600 subjects	
	Lower limit (LL)	Upper limit (UL)
1%	0.4	2.2
2%	1.0	3.5
3%	1.8	4.7
4%	2.6	5.9
5%	3.4	7.1
10%	7.7	12.7
15%	12.2	18.1
20%	16.9	23.4

\*: The symptom could be any one of expected AE, unexpected AE or SAE.

## 11.3. Study cohorts to be evaluated

### 11.3.1. Total Vaccinated cohort

The total vaccinated cohort will include all subjects who receive at least one dose of *Cervarix* in the PMS:

### 11.3.2. Total Safety cohort

Safety analysis based on all vaccination groups will include all subjects who were vaccinated per product information and have completed 30-day follow-up after at least one dose, regardless of the number of dose.

## 11.4. Conduct of analyses

Any deviation(s) or change(s) from the original statistical plan outlined in this protocol will be described and justified in the final PMS report.

**CONFIDENTIAL**208710 (EPI-HPV-077 VS KR PMS)  
Protocol Amendment 1 Final

#### **11.4.1. Sequence of analyses**

Analysis will be performed bi-annually for the first two years and annually for the remaining follow-up years (based on pre-defined cut-off date for enrolment). A comprehensive analysis will be performed at the end of the PMS. The analysis, including individual data listings, will be based on the cohort for vaccinated subjects for whom the PMS conclusion page has been received at GSK before the pre-defined cut-off date.

Bi-annual PMS reports will be written for the first two years and annual PMS reports will be written for the remaining years. A comprehensive PMS report will be written at the end of the PMS. All analyses described will be performed on cleaned data for each bi-annual/annual report. All reports will be sent to the GSK Biologicals' Central Safety and Pharmacovigilance (VCSP) and to MFDS (Korea).

#### **11.4.2. Statistical considerations for interim analyses**

As this is a descriptive PMS there will be no statistical adjustments required for the each bi-annual/ annual analysis. The results of these analyses will not have an impact on the future PMS conduct.

### **11.5. Statistical methods (Amended: 14 May 2018)**

#### **11.5.1. Analysis of demographics/baseline characteristics**

Demographic characteristics (age, gender, and ethnicity) ***and weight, height*** of the PMS cohort will be tabulated using descriptive statistics. Mean, standard deviation, median, minimum and maximum will be calculated for continuous variables, and frequency and percentage will be calculated for categorical variables.

The medical history ***by disease classification and per past/current status*** and vaccination history of the vaccinated subjects will also be presented.

The distribution of subjects vaccinated among the PMS centres by years will be tabulated.

#### **11.5.2. Analysis of safety**

Safety analysis based on total vaccinated cohort, will include all subjects who were vaccinated per product information and have completed 30-day follow-up after at least one dose, regardless of the number of dose. Analysis of AE/SAE data reported after each dose will be performed separately.

**CONFIDENTIAL**208710 (EPI-HPV-077 VS KR PMS)  
Protocol Amendment 1 Final**11.5.2.1. Within group assessment**

The AEs/ SAEs will be analysed in the PMS report according to the expectedness and unexpectedness criteria. (Refer to **GLOSSARY OF TERMS** for the definitions of expected AEs and unexpected AEs).

The number and percentage, with exact 95% confidence interval (CI), of any AEs occurring within 30 days (**Day 1 to Day 30**) will be tabulated, for each dose, for overall doses and by number of subjects. The same calculations will be done for any adverse events according to the severity and for those assessed as causally related to vaccination.

The verbatim reports of signs and symptoms will be matched and coded according to the appropriate WHO-ART Preferred Term. The PMS physician will review and confirm the appropriate WHO-ART Preferred Term by responding to data queries if any discrepancies are reported while coding. The percentage of subjects with AEs occurring within 30 days (**Day 1 to Day 30**) with its exact 95% CI will be tabulated by preferred term. Similar tabulation will be done for AEs with relationship to vaccination and for AEs rated as grade 3.

The number and percentage of subjects who received concomitant medication/ vaccination at least once during the 30-day (**Day 1 to Day 30**) follow-up period will be tabulated after each vaccine dose and overall, with exact 95% CI. Similar tabulations will be done for the number of subjects by types of medication/ vaccination during the entire PMS period.

The outcome of pregnancy (reported in the pregnancy report form) for subjects who become pregnant subjects during PMS will be presented, If possible.

Serious adverse events and withdrawals due to adverse events reported during the PMS period (each subject receiving the vaccine up to 30 days after the last dose) will be described in detail.

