5.5 Other Statistical Considerations

The analysis will be performed considering the following, and if a separate consideration is required for each analysis item, the content will be described in section in 7.1 Derivation.

- All test statistics will be the results of two-sided test with the statistical significant level of 0.05.
- When calculating percentage in categorical variables in accordance with baseline background factor, the denominator will be defined by total number of subjects in each category. However, the denominator of detail items such as past / current medical history, Cervarix vaccination history, prior / concomitant medication, prior / concomitant vaccination will be defined by the number of subjects who recorded as 'Yes'.
- When calculating incidence proportion of adverse event in accordance with baseline background

factor, the denominator will be defined by the number of subjects in each category. However, the denominator of detail items such as past / current medical history, Cervarix vaccination history, prior / concomitant medication, prior / concomitant vaccination will be defined by the number of subjects in each category who recorded as 'Yes'.

- When calculating incidence proportion of adverse event such as adverse event, adverse drug reaction, serious adverse event, serious adverse drug reaction, unexpected adverse event, unexpected adverse drug reaction, unexpected serious adverse event, unexpected serious adverse drug reaction, unexpected non-serious adverse event and unexpected non-serious adverse drug reaction the denominator will be defined by the number of subjects in safety analysis set. Only in case of analysis by non-safety analysis set, the denominator is the number who does not include 'Subject who did not receive Cervarix' and 'Follow-up failure' of the total number of subjects excluded from safety analysis set.
- When calculating percentage in analysis of the variable collected only for some subjects such as pregnancy, the denominator will be defined by the number of subjects related with each variable.
- If the number of subjects with adverse event is less than 10, the analysis of incidence proportion of adverse event accordance with baseline background factor may be replaced with adverse event list.
- When more than 20% of expected frequency of the cell count is less than 5, Fisher's exact test should be used instead of Chi-square test.
- The 95% confidence interval will be estimated by using exact methods.

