7.2 Categorization

Categories for each item are as follows.

However, the following defined category for continuous variable can be changed according to the distribution of actual collected data.

| Item | Category |
|---------------------|--------------------------------|
| • Pediatric subject | < 18 years, \geq 18 years |
| • Geriatric subject | < 65 years, \geq 65 years |
| • Pregnant subject | Yes, No, NA |
| • Liver disease | Yes, No |
| • Renal disease | Yes, No |

| Item | Category |
|--|---|
| • Age | 9 ~ 14 years, 15 ~ 25 years |
| • Gender | Male, Female |
| • Ethnicity | Korean, Non-Korean |
| • Past medical history | Yes, No |
| • Current medical history | Yes, No |
| • Prior medication | Yes, No |
| • Concomitant medication | Yes, No |
| • Prior vaccination | Yes, No |
| • Concomitant vaccination | Yes, No |
| • Vaccination history of prior Cervarix | Yes, No |
| • Dose number of Vaccination history of prior Cervarix | Dose 1, Dose 1 and Dose 2 |
| • Total number of Cervarix vaccination in the PMS | One dose, Two doses, Three doses |
| • Order of Cervarix vaccination | 1st dose, 2nd dose, 3rd dose |
| • Site | Non-Administration site, Administration site |
| • Outcome | Recovered, Not recovered, Recovering, Resolved with sequelae, Fatal (SAEs only), Unknown |
| • Maximum intensity | Mild, Moderate, Severe |
| • Relate to Cervarix | Certain, Probable / Likely, Possible, Unlikely, |

| Item | Category |
|--------------------------|---|
| | Conditional / Unclassified, Unassessable / Unclassifiable |
| • Medical attended visit | None, Hospitalization, Emergency Room, Medical Personnel |

References

The minister of Food and Drug Safety. Practical guideline for re-examination of new drugs. 2012

GlaxoSmithKline (GSK). A prospective, observational, multi-centre, post-marketing surveillance (PMS) to monitor the safety of GlaxoSmithKline (GSK) Biologicals' human papillomavirus (HPV)-16/18 vaccine, Cervarix when administered to 9-25 years old subjects according to the approved Prescribing Information in Korea.

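### The exact interval on the protocol's overall-dose AE percentage treats repeat doses in one subject as independent, so it is too narrow if AEs cluster within subject

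*Protocol*

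**What the plan says.** Protocol 11.5.2.1 (Within group assessment) specifies "The number and percentage, with exact 95% confidence interval (CI), of any AEs occurring within 30 days", and adds that these "will be tabulated, for each dose, for overall doses and by number of subjects". It then asks for the same calculations by severity and for AEs judged causally related, so the overall-dose row recurs in those tables. The next paragraph, on preferred terms, names subjects as the unit: "The percentage of subjects with AEs occurring within 30 days".

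The planned precision in Protocol 11.2 is also per subject. Table 6 gives the "exact two-sided 95% confidence interval for a sample size of 600 subjects".

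SAP 5.5 states a general rule: "The 95% confidence interval will be estimated by using exact methods". The same section sets the denominator of AE incidence proportions as the number of subjects in the safety analysis set (or the corresponding number of subjects for the non-safety set). SAP 6.8.1 reports numbers of subjects and analyses each dose separately. SAP 6.8.2 counts a subject once per category. No section of the SAP names a percentage of pooled doses.

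The number of doses a subject receives within the surveillance varies. SAP 7.2 tabulates "One dose, Two doses, Three doses", and Protocol section 3 allows entry at any stage whatever doses were given before.

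**The concern.** The protocol lists overall doses as a level separate from subjects, so the natural unit of that row is the dose. The exact binomial interval is valid when the units are independent. Doses given to the same person are not obviously so: the same subject or parent fills in the diary after each dose, and the site physician grades intensity and causality. If someone who reports an AE after one dose is more likely to report one after the next, the pooled doses carry less information than their number suggests. The interval labelled 95% then covers less often than 95%.

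AE frequency is the stated objective, and the reports go to the MFDS. At stake is overstated precision on one row of the AE summary and on its repeats by severity and causality. Neither document specifies an adjustment.

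**Working it through.** **Inputs from the documents.** Subjects: 600 (Protocol 11.2: "at least 600 evaluable subjects will be recruited for the PMS"). Interval: exact, two-sided, 95%. Doses per subject in the surveillance: one, two or three, with no distribution given.

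**Assumptions.** The documents give neither an ICC nor a dose mix. I take ICC 0.1, 0.3 and 0.5, an AE rate of 10% per dose, and three dose patterns: two doses each, three doses each, and an illustrative mix of 20/40/40% with one, two and three doses.

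**Step 1: reproduce the plan's own figure.** The Clopper-Pearson limits for x events in n units are the 2.5% quantile of Beta(x, n-x+1) and the 97.5% quantile of Beta(x+1, n-x). With n = 600, all eight rows of Table 6 are reproduced. For example, 10% gives 7.7 to 12.7 and 20% gives 16.9 to 23.4. Table 6 is correct, and it is a per-subject table.

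**Step 2: design effect.** With m doses per subject, DE = 1 + ICC x (sum of m² / sum of m - 1). For equal m this is 1 + (m-1) x ICC. For the mix, 120 x 1 + 240 x 2 + 240 x 3 = 1,320 doses and 120 x 1 + 240 x 4 + 240 x 9 = 3,240. Since 3,240/1,320 = 2.45, DE = 1 + 1.45 x ICC. The correct interval is about √DE times as wide as the unadjusted one.

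| Doses per subject | Pooled doses | DE at ICC 0.1 / 0.3 / 0.5 | √DE |
|---|---|---|---|
| 2 | 1,200 | 1.10 / 1.30 / 1.50 | 1.05 / 1.14 / 1.22 |
| 20/40/40 mix | 1,320 | 1.15 / 1.44 / 1.73 | 1.07 / 1.20 / 1.31 |
| 3 | 1,800 | 1.20 / 1.60 / 2.00 | 1.10 / 1.26 / 1.41 |

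**Step 3: intervals at a 10% rate.** The unadjusted interval uses all pooled doses. The adjusted one is Clopper-Pearson on pooled doses divided by DE.

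| Doses per subject | Unadjusted | ICC 0.1 | ICC 0.3 | ICC 0.5 |
|---|---|---|---|---|
| 2 | 8.36-11.84 | 8.28-11.94 | 8.14-12.12 | 8.01-12.29 |
| 3 | 8.65-11.48 | 8.53-11.63 | 8.31-11.90 | 8.12-12.15 |

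At the extreme of ICC 1 with three doses each, 1,800/3 = 600, and the interval becomes Table 6's 7.7 to 12.7.

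**Step 4: coverage of the unadjusted interval.** These figures come from beta-binomial simulation with 600 subjects and a 10% rate.

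| Doses per subject | ICC 0.1 | ICC 0.3 | ICC 0.5 |
|---|---|---|---|
| 2 | 94-95% | 92% | 90% |
| 20/40/40 mix | 94-95% | 91% | 87% |
| 3 | 93% | 88-89% | 84-85% |

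With ICC 0, coverage is just over 95% and nothing is wrong. At a 1% rate and ICC 0.1 it stays at about 95% with two or three doses each, because the exact method is conservative at low counts. With three doses and a 10% rate the shortfall becomes material from an ICC of about 0.2, where coverage is about 91%.

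**The case against.** The strongest reply is that the row may never be produced. The SAP details the reported analysis, uses subject denominators throughout its AE proportions, and contains no pooled-dose percentage. Its mock-up tables are not shown, so this cannot be settled. The dose denominator in the protocol is itself an inference.

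Most of this stands, and it limits the point. A reader might infer from the general rule in SAP 5.5 that the SAP repeats the fault in every interval. It does not: an exact binomial CI suits the per-subject proportions that the SAP lists. The omission does not close the matter, however. The SAP says that it is based on the protocol's method and nowhere says that the row is dropped, while Protocol 11.4 requires deviations from the protocol's statistical plan to be described and justified in the final report.

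A second reply is that the three-dose figures are a worst case. That also stands. Ages 9-14 may follow a two-dose schedule, subjects may enter after earlier doses, and completion needs follow-up after only one dose (Protocol 3 and 10.1). Coverage of 84-85% should therefore not be read as what this surveillance will deliver. It needs three doses in every subject and an ICC of 0.5, and the documents support neither.

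A third reply is that little hangs on the interval. Protocol 11.4.2 calls the surveillance descriptive and says that periodic results will not affect its conduct. Valid per-dose and per-subject intervals sit in the same tabulation. This is a reason to rate the point low, but it does not justify labelling an interval 95% when its method does not fit its unit.

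**Conclusion.** The point holds for the overall-dose row of Protocol 11.5.2.1 and its repeats by severity and causality. It is conditional on the pooled-dose reading, on more than one dose per subject, and on positive within-subject correlation. Under the assumed ICCs of 0.1 to 0.5, the correct interval is about 5-22% wider with two doses each, 7-31% with the illustrative mix and 10-41% with three. The effect is negligible at low correlation, and at a 1% rate with ICC 0.1. No other listed AE interval is affected, and no test or decision depends on this one. Severity is minor. The mismatch between protocol and SAP over whether the row exists needs resolving in any case.

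**What to change.** In Protocol 11.5.2.1, state whether the overall-dose row is still planned.

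- **If it is planned,** define its denominator as doses given within the surveillance. For this row and its severity and causality repeats, replace the exact binomial CI with one that clusters on subject. This can be Clopper-Pearson on the effective number of doses (pooled doses divided by an estimated design effect) or GEE with a robust standard error by subject. State a fallback for zero or sparse counts, where a GEE logit has no finite estimate or is unstable and the design effect cannot be estimated reliably. The per-subject exact CI can serve, labelled as per subject because it describes a different proportion. Add the row and its method to the SAP.
- **A simpler alternative** is to report the pooled-dose percentage without a CI and rely on the per-subject exact CI beside it.
- **If it is dropped,** say so in the SAP and justify the deviation as Protocol 11.4 requires.

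Keep Clopper-Pearson for the per-dose and per-subject rows. The cost is about a sentence in each document and a few lines of code. The downside is a somewhat wider interval on that row that is no longer exact.
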